14.3.2 Main Secondary Endpoint Analysis

• The secondary endpoints will be composed of two families. The first family consists of the composite endpoint of MACCE (CV death, MI, stroke) plus BARC bleeding (type 2, 3, or 5). The second family will consist of MACCE plus BARC bleeding (type 3, or 5), MACCE, and BARC bleeding (type 2, 3, or 5). The endpoints from the second family will be tested hierarchically, thereby maintaining the study-wise alpha level. These secondary endpoints will only be tested if both the primary composite endpoint and BARC bleeding are significant at non-inferiority analysis, and superiority analysis. Composite endpoint of MACCE plus BARC bleeding (type 3, or 5) will be tested first, and only if this is significant, the composite endpoint of MACCE only will be tested afterwards. BARC bleeding (type 2, 3, or 5) will be tested only if both of the above endpoints are tested significant.

14.3.3 Exploratory Test Variable Analysis

For continuous data, present technical statistics (mean, standard deviation, median, min. and max. value) on the changes between base & each visits. Based on whether the data follow normal distribution, comparatively verify between the two groups using the independent t-test or Wilcoxon's rank sum test. Also, for comparison within each group, analyze using the paire d t-test or Wilcoxon's signed rank test. For categorical data, present technical statistics (fre quency, percentage) and comparatively verify between groups using the chi-square test or Fisher's exact test.

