9.2. Study Design

Screening period

To conduct screening AMI patients based on the inclusion/exclusion criteria who (1) have been treated with ticagrelor + aspirin for at least 30±7 days after an index PCI, (2) received full explanation of the study details, (3) given written consent.

To randomize eligible subjects within 30±7 days after AMI undergoing PCI with newer ge neration DES, and receiving aspirin and ticagrelor to the treatment and control groups in a 1:1 ratio.

Treatment period

Enrolled patients receive clopidogrel 75mg + aspirin 100 mg (treatment group) or ticagrelor 90mg bid +aspirin 100mg treatment (control group) for 11 months (post-AMI 1 month to 12 months) and evaluation safety and efficacy by conducting physical examination, checking vital sign, and collecting adverse events at post-PCI 3M, 6M, 12M visits.

Laboratory and imaging tests, which undergo according to the medical judgment of each investigator during the study period, are collected by reviewing medical records or EMR.

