	Clinical definition of probable stent thrombosis is considered to have occurred			
	after intracoronary stenting in the following cases:			
	Any unexplained death within the first 30 days§			
Probable	Irrespective of the time after the index procedure, any MI that is related to			
	documented acute ischemia in the territory of the implanted stent without			
	angiographic confirmation of stent thrombosis and in the absence of any			
	other obvious cause			
*Definite stant thrombo	nois is considered to have occurred by either angiographic or nathological confirmation			

- *Definite stent thrombosis is considered to have occurred by either angiographic or pathological confirmation.
- †The incidental angiographic documentation of stent occlusion in the absence of clinical signs or symptoms is
- not considered a confirmed stent thrombosis (silent occlusion).
- 561 ‡Intracoronary thrombus.
- §For studies with ST-elevation MI population, one may consider the exclusion of unexplained death within 30
- days as evidence of probable stent thrombosis.
- 564 7.1.5.
- **10.2.5. Safety monitoring**
- 566 **10.2.5.1.** Vital Sign
- At every visit, measure vital sign (blood pressure, pulse and respiratory rate measured sitting down
- 568 for 5 min.)

569

570 **10.2.5.2. Physical Examination**

- 571 Physical examination should be conducted at every visit. Physical examination includes allergies,
- 572 cardiovascular, lung/respiratory, gastrointestinal/liver, biliary, metabolic/endocrine, nephritic/urinary,

573 reproductive, musculoskeletal, skin/connective tissues, neurological, psychic and other physical 574 organs. Results of clinical importance should be recorded in the comment box of the case report 575 form. In case there are incidences of medical importance according to the adverse events definition 576 after the test drug treatment, it should be recorded as adverse events in the case report form.

577 578

581

10.2.5.3. **Adverse Event**

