10.3. Visit schedule and assessment

661

662 10.3.1. 1st Visit (Screening, -30D ~ -1D)

- Subject written consent
- 2) Demographic/Physical examination
- 665 3) Medical history
- 666 4) Current medication
- 5) Dyspnea evaluation
- 668 6) Pregnancy test
- 669 7) Vital sign
- 670 8) Physical examination
- 671 9) Subject suitability test
- 10) Exploratory test (Optional): Lab test, Cardiac Echo, ECG

673674

10.3.2. 2nd Visit (Baseline, 1D, PCI 1M)

- 1) Efficacy test: CV death, MI, Stroke, BARC bleeding (type 2, 3, or 5), Cardiac death, Death from any cause, Death from vascular cause, Acute MI, Stent thrombosis, Ischemia Driven
- 677 Revascularization

- 678 2) Vital sign 679 3) Physical examination 680 4) Adverse event test 681 5) Dyspnea evaluation 682 6) Investigational drug prescription 683 7) Combined medication change 684 8) Subject suitability test 9) Randomize number given 685 686 10) Exploratory test (Optional): Lab test, Cardiac Echo, ECG 687 688 10.3.3. 3rd Visit (Treatment, 2M, PCI 3M) 689 1) Efficacy test: CV death, MI, Stroke, BARC bleeding (type 2, 3, or 5), Cardiac death, Death 690 from any cause, Death from vascular cause, Acute MI, Stent thrombosis, Ischemia Driven 691 Revascularization 692 2) Vital sign 693 3) Physical examination 694 4) Adverse event test 695 5) Dyspnea evaluation 696 6) Investigational drug prescription 697 7) Adherence Assessment 698 8) Combined medication change 699 9) Exploratory test (Optional): Lab test, Cardiac Echo, ECG 700 701 10.3.4.4th Visit (Treatment, 5M, PCI 6M) 702 1) Efficacy test: CV death, MI, Stroke, BARC bleeding (type 2, 3, or 5), Cardiac death, Death 703 from any cause, Death from vascular cause, Acute MI, Stent thrombosis, Ischemia Driven 704 Revascularization 705 2) Vital sign 706 3) Physical examination 707 4) Adverse event test 708 5) Dyspnea evaluation 709 6) Investigational drug prescription
- 710 7) Adherence Assessment
- 711 8) Combined medication change
- 712 9) Exploratory test (Optional): Lab test, Cardiac Echo, ECG

714	10.3.5.5th Visit (Treatment, 11M, PCI 12M)
715	1) Efficacy test: CV death, MI, Stroke, BARC bleeding (type 2, 3, or 5), Cardiac death, Death
716	from any cause, Death from vascular cause, Acute MI, Stent thrombosis, Ischemia Driven
717	Revascularization
718	2) Vital sign
719	3) Physical examination
720	4) Adverse event test
721	5) Dyspnea evaluation
722	6) Adherence Assessment
723	7) Combined medication change

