14.3.5.2 Vital sign, physical examination

For continuous data, present technical statistics (mean, standard deviation, median, min. and max. value) on the changes between base & each visits. Based on whether the data follow normal distribution, comparatively verify between the two groups using the independent t-test or

Wilcoxon's rank sum test. Also, for comparison within each group, analyze using the paired t-test or Wilcoxon's signed rank test. For categorical data, present technical statistics (frequency, percentage) and comparatively verify between groups using the chi-square test or Fisher's exact test.

925 926

922

923

924

927 928

929

930

931

932

933

934

935

Safety (including side-effects) Evaluation Standard, Method and Reporting

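### Vital-sign and exploratory changes are compared between arms without baseline as a covariate, by a test picked on whether the data look normal; this loses precision but causes no bias

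*Protocol*

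**What the plan says.** Section 14.3.3 (Exploratory Test Variable Analysis) asks for summary statistics "on the changes between base & each visits". It then tells the analyst to "comparatively verify between the two groups using the independent t-test or Wilcoxon's rank sum test", with the choice made "Based on whether the data follow normal distribution". Paired tests within each arm follow: a paired t-test or a signed-rank test.

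Section 14.3.5.2 (Vital sign, physical examination) repeats the method: "comparatively verify between the two groups using the independent t-test or" the rank-sum test. The same two paragraphs stand in the Statistical Analysis part of the Protocol Summary, under the exploratory and the safety variables. Section 8.7 (General Statistical Methodology) names t-tests or analysis of variance, with the rank-sum test where normality fails. None of these places adjusts for the baseline value.

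On what is collected, section 10.2.5.1 says "At every visit, measure vital sign (blood pressure, pulse and respiratory rate measured sitting down" for five minutes, so vital signs are available at V2, the visit labelled Baseline. Section 10.3 lists the others at each visit as "Exploratory test (Optional): Lab test, Cardiac Echo, ECG". Section 9.2 describes laboratory and imaging tests as ones "which undergo according to the medical judgment of each investigator during the study period", and collects them from medical records.

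**The concern.** A change score fixes the slope of follow-up on baseline at 1. When the true slope is smaller, subtracting the whole baseline adds noise to the between-arm comparison. Using baseline as a covariate lets the data set the slope and removes that noise at no cost in data. What is at stake is the width of the intervals on the between-arm differences in vital signs and, where measured, laboratory, echo and ECG variables.

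Two smaller matters come with it:

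- The choice between t-test and rank-sum test depends on how the data look, and no way of judging this is given. Applied by variable and by visit, the rule could give the same variable a t-test at 3 months and a rank test at 12 months. The two tests do not address the same quantity, so the results would not line up across visits.
- The within-arm paired tests say nothing about the difference between arms. Change within one arm after a myocardial infarction mixes recovery with any drug effect.

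**Working it through.** **Inputs.** The documents give no sample size, standard deviation, effect size, correlation or power for any vital-sign or exploratory variable, so there is no planned figure to reproduce. The correlation rho between baseline and follow-up is an assumption, shown from 0.3 to 0.9.

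**Variance per patient**, with standard deviation 1 at both times:

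- change score: 1 + 1 − 2·rho = 2(1 − rho)
- follow-up value alone: 1
- ANCOVA, follow-up adjusted for baseline: 1 − rho²

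ANCOVA relative to change score: (1 − rho²) / [2(1 − rho)] = (1 + rho)/2.

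| rho | change score | ANCOVA | ratio (1+rho)/2 | variance lower by | standard error lower by |
|---|---|---|---|---|---|
| 0.3 | 1.40 | 0.91 | 0.65 | 35% | 19% |
| 0.5 | 1.00 | 0.75 | 0.75 | 25% | 13% |
| 0.7 | 0.60 | 0.51 | 0.85 | 15% | 8% |
| 0.9 | 0.20 | 0.19 | 0.95 | 5% | 2.5% |

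Read the other way, the change-score variance is 1.54, 1.33, 1.18 and 1.05 times that of ANCOVA.

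**Unequal variances.** With standard deviations s0 at baseline and s1 at follow-up, the change-score variance minus the ANCOVA variance is (s1² + s0² − 2·rho·s0·s1) − s1²(1 − rho²) = (s0 − rho·s1)². This is never negative. In large samples ANCOVA therefore does not lose, whatever the ratio of the standard deviations; only the size of the gain depends on it.

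**What is tested.** The sentence naming the tests does not itself repeat that the changes are compared, though that is the natural reading. If follow-up values alone were compared (variance 1), ANCOVA would have 0.91, 0.75, 0.51 and 0.19 of that variance at the same four correlations. The point holds on either reading.

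**What it means for power.** A simulation used 1,165 patients per arm (the efficacy number in section 7.3.1, borrowed for illustration), an assumed shift of 0.12 standard deviations, two-sided 0.05 and 2,000 runs. Power rose from 68% with the change-score t-test to 85% with ANCOVA at rho 0.3, from 82% to 92% at 0.5, and from 96% to 98% at 0.7.

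**Where a baseline exists.** It is assured for vital signs (section 10.2.5.1). Laboratory, echo and ECG results exist only where the test was done clinically (sections 9.2, 10.2.6 and 10.3). Type of AMI is known for every randomised patient, because it is a stratification factor (section 9.3.1).

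**The case against.** The strongest objection is that this is a preference about analyses that decide nothing. The variables are exploratory or descriptive safety measures outside the testing hierarchy of section 14.3.2, no precision target is missed, and covariate adjustment of such variables is usually left to the SAP. The first part stands and sets the importance: minor. The second does not, because the protocol does not stay silent. It prescribes a method in two sections and repeats it in the Summary.

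The size is also open to challenge. The correlation is assumed, the gain is only 5% of variance at rho 0.9, and the formula compares means, so it does not cover the rank-sum branch. All of this stands as a limit on the size.

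A reader might infer more than the text supports:

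- *That the baseline value is thrown away.* It is not. The plan subtracts it, and the paired tests use it too. What is missing is its use as a covariate.
- *That the comparison is biased by regression to the mean.* Allocation is randomised 1:1, stratified by centre and type of AMI, so the change-score comparison is unbiased over randomisation. A chance baseline difference affects the one realised trial, and with arms of about 1,295 it is likely to be small for vital signs.
- *That all these variables have a baseline.* Only vital signs surely do. For the others, who happens to be tested limits interpretation more than the choice of test, and ANCOVA does not cure that.
- *That the plan offers the paired tests as evidence of a treatment effect, or requires a formal normality test.* It gives the paired tests for within-arm comparison and leaves the way of judging normality open.

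**Conclusion.** The point holds as a minor loss of efficiency. The planned between-arm comparison is unadjusted, and under equal variances its variance exceeds that of baseline-adjusted ANCOVA by a factor 2/(1 + rho): substantial at low correlation, negligible near 1. It rests on an assumed rho and on a comparison of means. It does not touch the primary or main secondary endpoints, the sample size or the validity of the randomised comparison. For laboratory, echo and ECG variables it applies only to patients with a baseline value, a restriction that change scores share. Section 8.7 does not supply the missing adjustment.

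**What to change.** - For continuous vital signs, and for laboratory, echo and ECG variables in patients with a baseline value, use ANCOVA of the follow-up value (or the change) on arm, baseline and type of AMI. Report the adjusted mean difference with a 95% interval at each visit.
- Name in advance the variables to be log-transformed, instead of letting the look of the data choose the test.
- Label the within-arm paired comparisons as descriptive.
- Make the same edit in sections 14.3.3 and 14.3.5.2 and in both matching paragraphs of the Protocol Summary, and bring section 8.7 into line. Changing only some of them would create a contradiction.

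The cost is wording. No new data, visits or patients are needed, and the chi-square and Fisher tests for categorical data can stay as they are.

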Principal investigator	[name], Division of Cardiology, Department of Internal Medicine, Seoul St. Mary's Hospital, The Catholic University of Korea <appendix 1=""> *Clinical Trial Investigator (CI)</appendix>			
Institution	Appendix 1			
Study phase	4			
Study design	Prospective, multi-center, randomized, open trial			
Study Objective	To investigate the efficacy and safety of switching from ticagrelor to clopidogrel in stabilized patients with AMI with no adverse events during the first month after an index PCI			
Study Drug	Test drug: Clopidogrel (Pregrel) Control drug: Ticagrelor (Brilinta)			
Study Duration	Institutional Review Board approval (Oct. 17 th , 2013 to Dec. 31 st , 2020)			
Study Disease	Acute myocardial infarction: ST-segment elevation MI (STEMI) and non-ST-segment elevation MI (NSTEMI)			
Study Population	2590 (loss to follow-up: 10 %) • Test group: 1295 • Control group: 1295			
Subject Inclusion & Exclusion Criteria	 Inclusion Criteria 1) Age ≥ 18 years 2) Patients with AMI (STEMI or NSTEMI) who are administered ticagrelor for 30 days after successful PCI with newer-generation drug eluting stents (DES) *Definition of AMI follows the 3rd Universal Definition of MI. 3) Female patients with childbearing potential who agree to mandatory 			

- pregnancy test and have committed to using adequate contraception
- 4) Subjects who agree to the study protocol and the schedule of clinical follow-up, and provides informed, written consent, as approved by the appropriate IRB of the respective institution

Exclusion Criteria

- 1) Cardiogenic shock
- 2) Active internal bleeding, bleeding diathesis, or coagulopathy
- Gastrointestinal bleeding or genitourinary bleeding, hemoptysis, or vitreous hemorrhage within 2 months
- 4) Major surgery within 6 weeks
- 5) History of intracranial bleeding, intracranial neoplasm, intracranial arteriovenous malformation, or intracranial aneurysm
- 6) Anemia (hemoglobin < 10 g/dL) or platelet count of less than 100,000/mm³ at the time of screening
- 7) Concomitant treatment with oral anticoagulant agent (vitamin-K antagonists or novel oral anticoagulants such as dabigatran, rivaroxaban, apixaban, or edoxaban
- 8) Daily treatment with non-steroidal anti-inflammatory drugs (NSAIDs) or cyclooxygenase-2 inhibitors
- 9) Malignancy or life expectancy of less than one year
- 10) Moderate or severe hepatic dysfunction (Child Pugh B or C)

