Implement noninferiority validation based on the tolerance limit after collecting cumulative occurrence rate of MACCE (CV death, MI, stroke) + BARC bleeding (type 2, 3, or 5) post 1M-1Y PCI and checking 95% confidence interval of [Ticagrelor occurrence rate — Clopidogrel occurrence rate]. If the upper value of the 95% confidence interval is less than 3% of the noninferiority tolerance limit, Clopidogrel is perceived noninferior to Tricagrelor. Present the cumulative limit method, Kaplan-Meier curve and conduct log-rank test to check the difference between two groups.

2. Main Secondary Endpoint Analyses

• The secondary endpoints will be composed of two families. The first family consists of the composite endpoint of MACCE (CV death, MI, stroke) plus BARC bleeding (type 2, 3, or 5). The second family will consist of MACCE plus BARC bleeding (type3, or 5), MACCE, and BARC bleeding (type 2, 3, or 5). The endpoints from the second family will be tested hierarchically, thereby maintaining the study-wise alpha level. These secondary endpoints will only be tested if both the primary composite endpoint and BARC bleeding are significant at non-inferiority analysis, and superiority analysis. Composite endpoint of MACCE plus BARC bleeding (type 3, or 5) will be tested first, and only if this is significant, the composite endpoint of MACCE only will be tested afterwards. BARC bleeding (type 2, 3, or 5) will be tested only if both of the above endpoints are tested significant.

3. Exploratory Test Variable

For continuous data, present technical statistics (mean, standard deviation, median, min. and max. value) on the changes between base & each visits. Based on whether the data follow normal distribution, comparatively verify between the two groups using the independent t-test or Wilcoxon's rank sum test. Also, for comparison within each group, analyze using the paired t-test or Wilcoxon's signed rank test. For c ategorical data, present technical statistics (frequency, percentage) and comparatively verify between groups using the chi-square test or Fisher's exact test.

4. Additional analysis should be run including all occurred events if the drug is given continuously.

Safety Test Variable Analysis

1. Adverse Event

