10.2.6. Exploratory Test Items

- 588 Lab Test 10.2.6.1.
- 589 Based on the investigator's medical judgment, following test results including the medical records
- 590 should be recorded in the case report form. Most recent blood test, blood coagulation test, blood
- 591 chemical test should be recorded.
- 592 Myocardial biomarker is collected at PCI admission during screening and if conducted at every visit,
- 593 use the most recent result. Also collect thyroid function test if conducted.

594 595

Items of each test is as below.

596

- Blood Test: WBC, Neutrophil, Lymphocytes, Hemoglobin, Platelet, ESR
- 598 Blood Coagulation Test: INR, Fibrinogen
- 599 Blood Chemical Test: Glucose, Creatinine, AST, ALT, Total bilirubin, Alkaline phosphatase, y-GTP, Calcium, Phosphorus, LDH, CPK, Uric acid, Total cholesterol, Triglyceride, HDL-600
- 601 cholesterol, LDL-cholesterol, hsCRP
- 602 Glycosylated hemoglobin: HbA1c
- 603 Platelet Function Test: VerifyNow, PFA-100/200
- 604 Myocardial Damage Index Test: Maximum CK, Maximum CK-MB, Maximum Troponin I, 605 Maximum Troponin T, NT-proBNP, BNP
- 606 Thyroid Function Test: T3, free T4, TSH
- 607 Kidney Function Test: Cockcroft-Gault eCCr, MDRD eGFR

608 Cockcroft-Gault eCCr(ml/min) = (140-age) * (Weight in kg) / (72 * SCr) * (0.85 for 609 women) MDRD eGFR(mL/min/1.73m²) = $186 * (SCr)^{-1.154} * (Age)^{-0.203} * 0.742$ (for women) 610 611 10.2.6.2. **Cardiac Echo** 612 613 Collect below items if ECHO is conducted. 614 EF (Ejection fraction) 615 LVEDV (Left Ventricle end-diastolic volume) 616 LVESV (Left Ventricle end-systolic volume) 617 LVDd (diastolic left ventricular diameter) 618 LVDs (systolic LV diameter) 619 IVSd (diastolic interventricular septal wall thickness) 620 PWTd (diastolic posterior wall thickness) 621 RWT (Relative Wall Thickness) 622 LVM (Left Ventricular Mass) 623 S' (Systolic velocity of mitral annulus) 624 GLS (Global Left ventricular Strain) E (Peak early diastolic velocity) 625 626 A (Peak late diastolic velocity) 627 DT (Deceleration time) E' (Early diastolic velocity of mitral annulus) 628 629 RVSP (Right Ventricular systolic pressure) 630 LA diameter(Left Atrial diameter) • 631 LA volume index 632 peak TR regurgitation velocity 633 Tei index(Myocardial Performance Index) 634 635 10.2.6.3. **ECG** 636 Basic rhythm 637 Ventricular rate 638 PR interval 639 QRS duration 640 QT 641 QTc 642 QRS axis

643 644

645

646

647

648

649

650

651

652

653

654

655

656

657

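### Post-randomisation laboratory, echo and ECG results come only from patients tested on clinical judgment, so the between-arm and within-arm p-values in 14.3.3 should give way to description

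*Protocol*

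**What the plan says.** The protocol summary describes the design as "Prospective, multi-center, randomized, open trial", so the investigator knows the arm.

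On who is tested:
- Section 9.2: "Laboratory and imaging tests, which undergo according to the medical judgment of each investigator during the study period, are collected by reviewing medical records".
- Section 10.2.6.1 (laboratory): "Based on the investigator's medical judgment, following test results including the medical records" are to be recorded. The latest blood results are taken, and for the myocardial biomarker the site is to "use the most recent result".
- Section 10.2.6.2 (echo): "Collect below items if ECHO is conducted".
- Section 10.3 marks laboratory, echo and ECG as optional at all five visits.
- The time table (front of the protocol and section 10.1) marks the exploratory test at every visit. In its footnote the word optional follows the genetic test only.

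On analysis, section 14.3.3 takes changes from baseline at each visit and, for continuous data, would "comparatively verify between the two groups using the independent t-test or Wilcoxon's rank sum test". It continues: "for comparison within each group, analyze using the paired t-test or Wilcoxon's signed rank test". The summary (Exploratory Test Variable) has the same text. Section 14.1 does not impute missing values in planned analyses and offers last observation carried forward as a sensitivity analysis.

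**The concern.** Randomisation protects a comparison of everyone randomised, or of a subset chosen without regard to what happens afterwards. A haemoglobin or an echo ordered on clinical grounds after randomisation selects patients partly on their course.

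The protocol itself gives reasons why that course may differ by arm. Section 11 lists dyspnea as an expected effect of ticagrelor but not of clopidogrel. Section 18.1 says bleeding risk can be higher with ticagrelor. In the BARC table (section 10.2.4), a type 2 bleed can qualify because it prompted evaluation. The clinician who orders the test is also unmasked.

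A p-value on haemoglobin, renal function or ejection fraction could then be read as a randomised drug effect when part of the difference reflects who was tested. A within-arm paired test has no comparator at all, so it mixes any drug effect with the natural course after infarction.

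**Working it through.** The plan gives no figure to reproduce: no expected share tested, standard deviation or sample size for any exploratory variable. The check is a reading of the text plus three calculations.

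**1. Who enters the tests.** Testing is discretionary (9.2, 10.2.6, 10.3) and values are not imputed (14.1), so the tests in 14.3.3 run on measured patients. Carrying the last value forward does not repair this. A patient never retested is given a change of zero, and a patient with no baseline value still drops out.

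**2. How many tests the text allows.** The lists in 10.2.6 give 39 laboratory + 20 echo + 7 ECG = 66 variables.
- Between arms, over V3 to V5: 66 × 3 = 198. At 5% with no effect and no selection, 198 × 0.05 ≈ 10 would be positive by chance.
- Within arms: basic rhythm is categorical and gets no paired test, so at most 65 × 3 × 2 = 390.

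These are ceilings. The multiplicity they show is separate from the selection problem.

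**3. Haemoglobin illustration.** The bleeding rates are the planning values in 7.3.2 (ticagrelor 4.07%, clopidogrel 2.99%). The rest is assumed: all bleeders and 40% of others are tested, in both arms alike, and each bleeder falls by 2 g/dL.
- Bleeders among the tested, ticagrelor: 4.07 / (4.07 + 0.4 × 95.93) = 9.6%
- Bleeders among the tested, clopidogrel: 2.99 / (2.99 + 0.4 × 97.01) = 7.2%
- Difference among the tested, from unrounded shares: 2 × (0.0959 − 0.0715) = 0.049 g/dL
- Difference among all patients: 2 × (0.0407 − 0.0299) = 0.022 g/dL

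A common testing rule therefore enlarges a real difference 2.3-fold here, but the absolute error is only about 0.03 g/dL.

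**4. Simulation under no drug effect.** All inputs are assumed except 1,295 per arm: change score with SD 1, chance of being measured a logistic function of that score, two-sided t-test at 0.05 on measured patients, 4,000 runs. The slope is the log-odds of being measured per SD of change.

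| Share measured | Slopes in the two arms | False rejection | Spurious difference (absolute, SD) |
|---|---|---|---|
| 50% / 50% | 0 / 0 | 5.1% | 0.00 |
| 50% / 50% | 0.3 / 0.3 | 5.0% | 0.00 |
| 50% / 60% | 0.3 / 0.3 | 8.1% | 0.03 |
| 50% / 50% | 0.2 / 0.3 | 14.8% | 0.05 |
| 50% / 50% | 0.1 / 0.3 | 44.8% | 0.10 |
| 50% / 50% | 0 / 0.3 | 76.3% | 0.15 |
| 80% / 80% | 0 / 0.3 | 28.0% | 0.06 |

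If selection is the same in both arms and the drug has no effect, the between-arm error rate stays at 5%. It rises when the share tested, or the way testing follows the course, differs by arm.

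**The case against.** The strongest reply is that little rests on these variables. They are exploratory, rank below every primary and secondary endpoint, carry no alpha, and the clinical endpoints are adjudicated centrally. The statistical analysis text that follows the protocol in the same file lists no laboratory, echo or ECG endpoint (section 5.0) and no paired test in its general methods (section 8.7). Reporting numbers measured is often left to an analysis plan. This stands as a limit on importance. It does not remove the point, because the protocol itself fixes the tests in 14.3.3.

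Some stronger readings are not supported:
- A reader might infer that 14.3.3 assumes every patient is measured. It does not say so, and 14.1 points to analysis of those measured.
- A reader might infer that testing does differ by arm. Open-label conduct and the expected side effects make that plausible, but nothing in the documents shows it.
- A reader might take the 2.3-fold figure as a material bias. With about 550 and 541 patients tested (0.424 and 0.418 × 1,295) and an assumed SD of 1.0 to 1.5 g/dL, the standard error is about 0.06 to 0.09 g/dL. The chance of p < 0.05 is then only about 8% to 13%. The illustration also places an 11-month bleeding rate in one comparison and gives every bleeder a 2 g/dL fall, which BARC type 2 does not require.
- A reader might expect the within-arm tests to be significant in both arms whatever the drug. That cannot be known for 65 varied measures, and the baseline visit comes 30 ± 7 days after PCI, when some recovery has already passed.
- A reader might say testing happens only at the investigator's choice. Screening haemoglobin and platelets are needed for eligibility (7.2), and the time table marks exploratory tests at every visit.

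**Conclusion.** The point holds in limited form. By sections 9.2, 10.2.6 and 10.3, post-randomisation laboratory, echo and ECG data are a selected subset, and 14.3.3 prescribes significance tests on it. The between-arm p-values lack the protection of randomisation and may be biased if testing depends on the patient's course or differs by arm. The within-arm tests cannot isolate a drug effect.

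The size of any bias is unknown. The 5% to 76% range depends on assumed selection patterns, and the haemoglobin example is small. No primary or secondary conclusion changes. The time table and section 10.3 disagree on whether these tests are optional, and the extent of selection depends on how that is reconciled.

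**What to change.** - In 14.3.3 and the matching summary text, report the number and share of patients measured per arm and visit, and present laboratory, echo and ECG data descriptively.
- Drop the between-arm p-values for these data, or keep them only with an explicit statement that they are non-randomised and hypothesis-generating.
- Remove the within-arm paired tests from 14.3.3, from 14.3.5.2 and from the summary. Section 14.3.5.2 applies the same paired tests to vital signs, so it should not be exempt.
- Report numbers measured for vital signs too: V3 to V5 may be telephone calls, so these values are not assured for everyone.
- Reconcile the time table with sections 9.2, 10.2.6 and 10.3 on whether these tests are optional.

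The cost is protocol wording and somewhat less analysis, with no new data collection. What is lost is a set of exploratory p-values.
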